Given the in vitro performance of this novel, fiber-like hydrogel, it is therefore hypothesized that the device may be of benefit in patients with CIC and IBS-C, however, analysis of how it affects whole gut motility has not been conducted. This will be observed using wireless motility capsule (WMC) testing, a non-invasive diagnostic tool capable of measuring intraluminal pressure and pH through the whole GI tract, assessing both transit and contractility. WMC has been demonstrated as a safe, convenient, and reliable method of assessing whole gut transit after a dietary intervention in a more physiologic setting than traditional manometry or scintigraphy.

II. Specific Aims

This is a single center, randomized, double-blind, parallel-group, placebo-controlled pilot study. The purpose of the study is to evaluate the efficacy of the hydrogel capsule CSP01 vs active control (carboxymethylcellulose) vs placebo in accelerating colonic motility among patients with chronic idiopathic constipation. Patients who meet the Rome IV criteria for CIC or IBS-C and who meet the inclusion criteria will be offered participation in this study.

III. Subject Selection

This study aims to recruit 53 total subjects to be enrolled at one site, Massachusetts General Hospital. The 53 subjects that this study aims to recruit factors in a dropout rate of 15%, with a final sample size of 45 subjects.

INCLUSION/EXCLUSION CRITERIA:

Inclusion

1. Age 22-70 years old
2. BMI >18.5 and <35 kg/m²
3. Rome IV criteria for functional constipation or IBS-C
4. Continued IBS-C or CIC throughout Run-in period
5. Compliant with reporting during Run-in (confirm the presence of constipation during the 7-day Run-in baseline period; patients are required to report an average of <3 continuous spontaneous bowel movements [CSBMs] and ≤6 spontaneous bowel movements [SBMs] per week via the interactive web response system).

6. Ability to follow verbal and written instructions
7. Ability to record daily bowel habits, including frequency, stool consistency (BSFS), straining (EoPS), completeness of evacuation, and Patient Reported Outcomes (PROs) (abdominal discomfort, severity of constipation, bloating, overall relief)
8. Informed consent form signed by the subjects

Exclusion

1. History of loose stools
2. History of irritable bowel syndrome with diarrhea (IBS-D) or mixed irritable bowel syndrome (IBS-M)
3. Non-compliance with reporting during Run-in

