4. Patients reporting laxative, enema, and/or suppository usage for >2 days or any usage of a prohibited medication during the Run-in period
5. Patients reporting watery stools for any SBM (Type 7 on the Bristol Stool Form Scale [BSFS]) or loose (mushy) stools for >1 SBM (Type 6 on the BSFS) in the absence of laxatives during Run-in
6. GI motility obstruction or GI tract structural abnormality
7. Current use of prescribed or illicit opioids
8. History of pelvic floor dysfunction
9. Need for manual maneuvers in order to achieve a BM
10. History of GI lumen surgery at any time or other GI or abdominal operations within 60 days prior to entry into the study
11. History of high-dose stimulative or cathartic laxative abuse as judged by investigator team
12. Neurological disorders, metabolic disorders, or other significant disease that would impair their ability to participate in the study
13. Cardiovascular disease, diabetes, cancer, Crohn's disease, ulcerative colitis
14. BMI of <18.5 or >35 kg/m²
15. Pregnancy (or positive serum or urine pregnancy test(s) in females of childbearing potential) or lactation
16. Absence of contraception in females of childbearing potential
17. History of allergic reaction to carboxymethylcellulose, citric acid, sodium stearyl fumarate, raw cane sugar, gelatin, or titanium dioxide
18. Administration of investigational products within 1 month prior to Screening Visit
19. Exclusion of colonic inertia with symptoms of < 1 BM per 2 weeks
20. Subjects anticipating surgical intervention during the study
21. Known history of diabetes (type 1 or 2)
22. History of eating disorders including binge eating (except mild binge eater)
23. Supine SBP > 160 mm Hg and/or supine DBP > 95 mm Hg (mean of two consecutive readings)
24. Angina, coronary bypass, or myocardial infarction within 6 months prior to Screening Visit
25. History of swallowing disorders
26. Esophageal anatomic abnormalities (e.g., webs, diverticuli, rings)
27. History of gastric bypass or any other gastric surgery

28. History of small bowel resection (except if related to appendectomy)
29. History of gastric or duodenal ulcer
30. History of gastroparesis
31. History of abdominal radiation treatment
32. History of pancreatitis
33. History of intestinal stricture (e.g., Crohn's disease)
34. History of intestinal obstruction or subjects at high risk of intestinal obstruction including suspected small bowel adhesions
35. History of malabsorption
36. History of sucrose intolerance

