In addition to patients of MGH, subjects from the general greater Boston population will also be recruited. Subjects from the general population will be recruited through online advertisements run using the Galen Recruitment Service. Through this service, respondents will be filtered by qualifying questions. Contact information for qualified respondents will be provided to research study staff.

IV. Subject Enrollment

a.) Methods of enrollment

1. Patients may be approached by a research coordinator in the Neurointestinal Health clinic if they have a history of chronic constipation and agree to hear more about the trial
2. Patients may be called by the research coordinator prior to their appointment and asked if they would like to hear more about the trial
3. Any patients agreeing to hear more about the trial will learn more before beginning the informed consent process should they agree to participate as well as determining whether they meet all of the inclusion criteria
4. Patients may be contacted about the research study by their MGH physician on behalf of the research team. Afterward, patients may then be contacted by the research team directly.
5. Subjects who have provided their contact information through internet advertising may be contacted by the research team directly.

b.) Procedures for obtaining informed consent

1. Patients agreeing to participate will sign an informed consent with the study doctor at the time of enrollment, after proper informed consent has been provided by the site.

c.) Treatment assignment and randomization

1. Patients who have been enrolled and consented in the trial will be randomized with a ratio of 1:1:1 with 15 subjects per arm: 15 subjects on 3 capsules BID of CSP01, 15 subjects on 3 capsules BID (morning, evening) of carboxymethylcellulose (CMC), and 15 subjects on 3 capsules BID of placebo (sucrose).
2. We will stratify by Rome IV diagnosis of CIC vs. IBS-C to avoid clustering of IBS-C patients in one group.
3. The study personnel and patients will be blinded to treatment allocation.
4. Patients who fulfill study admission criteria and have a signed consent form will be assigned a 3-digit sequential patient number. The number will be used throughout the study.

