 - c. Matching placebo consists of an inert mixture supplied by the Sponsor in identical-appearing capsules
2. Rescue medications (in case of emergency)
 - a. If a subject experiences inadequate prevention of constipation while on the study treatment or placebo, the patient may be administered a rescue medication (laxative) at the discretion of the patient conferring with the Study physician or research NP consistent with “prn” orders or new orders from the medical team. Drugs that are available to treat constipation include: Colace (Docusate), Polyethylene glycol (Miralax), Senna (Senokot), magnesium citrate, and lactulose. Because constipation is not a side effect of the medication, all patients will be able to receive laxative doses as needed at their request throughout the study consistent with nurse’s or physician’s discretion without restriction.
 - b. Patients with no bowel movement for 5 consecutive days, who are in need of a rescue treatment, will be instructed to contact the investigator. The following treatment is recommended, as applicable, in the following order:
 - i. 1. Glycerin suppository
 - ii. 2. Enema
 - iii. 3. Laxadin/Bisacodyl tablets (3x5mg)
 - c. Administration of rescue treatment is at the discretion of the investigator based on an assessment of the subject; administration of rescue should be monitored and recorded.

c.) Data to be collected and timeline for collection

1. Primary endpoints
 - a. Colonic Transit Time (CTT)
2. Secondary endpoints
 - a. Spontaneous Bowel Movement (SBM) frequency rate
 - b. Complete Spontaneous Bowel Movement (CSBM) frequency rate
 - c. Stool consistency (Bristol Stool Form Scale)
 - d. Straining (Ease-of-Passage Scale)
 - e. Abdominal discomfort (Self Assessment on 0–10-point numerical rating scale)
 - f. Bloating (Self Assessment on 0–10-point numerical rating scale)
 - g. Constipation severity (Self Assessment on 0–10-point numerical rating scale)
 - h. Overall relief (Self Assessment on 0–10-point numerical rating scale)
 - i. Balloon Expulsion Time (BET) before and after
 - j. PAC-SYM change
 - k. PAC-QOL change
 - l. Need for rescue laxatives

c.) Adverse events

1. Definition of adverse events

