2. Specific data to be collected through patient-reported questionnaires
 - a. Spontaneous Bowel Movement (SBM) frequency rate
 - b. Complete Spontaneous Bowel Movement (CSBM) frequency rate
 - c. Stool consistency (Bristol Stool Form Scale)
 - d. Straining (Ease-of-Passage Scale)
 - e. Abdominal discomfort (Self Assessment on 0–10-point numerical rating scale)
 - f. Bloating (Self Assessment on 0–10-point numerical rating scale)
 - g. Constipation severity (Self Assessment on 0–10-point numerical rating scale)
 - h. Overall relief (Self Assessment on 0–10-point numerical rating scale)
 - i. Balloon Expulsion Time (BET) before and after
 - j. Constipation symptom severity (PAC-SYM)
 - k. Constipation quality of life (PAC-QOL)
 - l. Need for rescue laxatives
3. Study endpoints – As above
4. Statistical methods
 - a. Analysis populations
 - i. Intent-to-treat (ITT) population: all patients who are randomized will be included in the ITT population. This will be the primary population for all analyses of demographics, patient characteristics and disposition, and efficacy data.
 - ii. Safety population: All patients who are randomized and receive any study treatment will be included in the safety population. This will be the primary population for all analyses of safety data
 - iii. Per-Protocol (PP) population: All patients who are randomized and receive the study medication on each day of their hospitalization. Major protocol violations include the following:
 1. Prohibited concomitant medication usage (specifically standing laxatives during hospitalization)The PP population may be used for supplementary analysis of selected efficacy and safety data, as appropriate.
 - b. Endpoint analyses
 - i. Primary endpoint: Colonic transit times will be compared in a paired fashion for individual patients before and after the intervention by means of a repeated measures ANOVA using a 3x2 design to distinguish between the outcomes of the three different groups. We will also use multivariable linear regression to compare change in transit time after adjusting for confounders, specifically: presence of IBS-C, abnormal balloon expulsion testing indicating dyssynergic defecation ($BET \geq 2$ minutes), age, and sex.

ii. Secondary endpoints: The secondary endpoints will be compared in a similar fashion, with logistic regression adjusting for confounders.

c. Power analysis

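### If rescue laxative use is coded yes/no, the planned adjusted logistic regression has at most 3.7 events per slope, and no small-sample method is named

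*Combined protocol and SAP*

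**What the plan says.** Section VI, item 4.b.ii gives one sentence for all twelve secondary endpoints: "The secondary endpoints will be compared in a similar fashion, with logistic regression adjusting for confounders". It lists no confounders of its own. The only list is in item 4.b.i, for colonic transit time: "adjusting for confounders, specifically: presence of IBS-C, abnormal balloon expulsion testing indicating dyssynergic defecation" (a balloon expulsion time, BET, of 2 minutes or more), then age and sex.

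The endpoint appears only by name, "Need for rescue laxatives", in section V.c (data to be collected), item 2.l, and again in section VI, item 2.l. No coding, time window or expected rate is given. On access, section V.b, item 2.a says that "all patients will be able to receive laxative doses as needed at their request throughout the study".

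On size, section III says: "The 53 subjects that this study aims to recruit factors in a dropout rate of 15%, with a final sample size of 45 subjects". Section IV.c, item 1 has patients "randomized with a ratio of 1:1:1 with 15 subjects per arm". The primary efficacy population is everyone randomised.

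Section VI names no exact, penalised or reduced model. Its power analysis covers colonic transit time only.

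**The concern.** Ordinary logistic regression behaves badly when the smaller outcome class is small relative to the number of slopes. Either some combination of terms predicts the outcome perfectly, so that an odds ratio is infinite and its interval meaningless (separation), or the fit converges with estimates that tend to lie too far from zero.

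Rescue use by arm matters more than its place at the end of the list suggests. The on-treatment motility test (capsule on Day 15, monitor returned on Day 22) falls in a period when laxatives are available on request. Section VI, item 4.c also hopes to combine transit with the secondary endpoints to derive a threshold for later research. A reader needs to know how far the results in each arm were obtained with laxatives, and an unusable or inflated odds ratio would not show it.

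**Working it through.** **The plan's own figures.** The group-by-time test in a 3x2 design equals a one-way ANOVA on change. Variance of change = 2 x 12² x (1 - 0.7) = 86.4. With mean changes of 0/10/13 h and 15 per arm, the noncentrality is 15 x 92.67/86.4 = 16.1. At alpha 0.05 (assumed; the text states none) power is 94.3%, against the stated 94%. The other figures also reproduce: 79.8% with 30 patients (stated 80%), 88.2% with a 1 h extra effect (stated 88%), and 45/0.85 = 52.9, so 53 recruited. None of these concerns rescue use.

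**Events per slope.** Two arm terms plus IBS-C, BET, age and sex make six slopes. With 45 patients the smaller outcome class is at most 22, and 22/6 = 3.7. At 20% overall use there are 9 events, and 9/6 = 1.5. If all 53 are analysed the ceiling is 26/6 = 4.3.

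**Sparse arms.** P(no user among 15) = (1 - p)^15: 46% at p = 5%, 21% at 10%, 9% at 15%, 1% at 25%.

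**Simulation.** 15 per arm, 1,500 trials per setting. Assumed, not in the documents: IBS-C 40%, female 75%, odds ratio 1.5 per binary covariate and half that log odds per SD of age. Paired values are for abnormal BET in 10% / 30% of patients. ML is ordinary maximum likelihood.

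| Placebo/CMC/CSP01 rates (overall) | Six-slope ML: no finite fit, % | Arm coefficient not finite, % | Arm-only ML: no finite fit, % | Six-slope ML, mean/true log OR, CMC | Same, CSP01 |
|---|---|---|---|---|---|
| 20/10/5% (12%) | 82.1 / 72.5 | 57.5 / 57.3 | 57.1 / 56.7 | 1.08 / 1.08 | 0.80 / 0.77 |
| 30/20/10% (20%) | 54.0 / 35.7 | 24.5 / 22.5 | 23.6 / 21.9 | 1.19 / 1.18 | 1.03 / 1.01 |
| 40/25/15% (27%) | 35.9 / 16.2 | 10.5 / 8.9 | 9.5 / 8.5 | 1.22 / 1.27 | 1.14 / 1.15 |
| 50/35/25% (37%) | 21.9 / 3.9 | 2.2 / 1.5 | 1.7 / 1.3 | 1.24 / 1.27 | 1.18 / 1.21 |
| 60/45/30% (45%) | 19.1 / 2.2 | 1.0 / 0.7 | 0.7 / 0.6 | 1.19 / 1.23 | 1.19 / 1.21 |

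The ratios use only the trials that could be fitted. With covariate odds ratios varied from 1 to 2, failure was 29-60% at 30/20/10% or 30/15/15%, and 16-41% at 40/25/15%. Exaggeration was 16-29% at overall rates of 37% or more.

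A run with other prevalences (IBS-C 35%, BET 25%) failed in 34% of trials at 30/20/10% and 16% at 40/25/15%. At 50/35/25% its mean CSP01 log odds ratio was -1.35 against a true -1.10 (odds ratio 0.26 against 0.33), with SD 1.07.

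**Firth regression, same six slopes.** It gives a finite estimate whenever some but not all patients use rescue. In the settings tabulated, its mean was within -2% to +8% of the truth at overall rates of 20% or more. At 20/10/5% it understated the CSP01 effect by 14-15%.

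**The case against.** The strongest reply is that much of this is inferred. Days or doses of laxative fit the endpoint's name as well as yes/no does, and the covariate list is borrowed from the primary endpoint. If dropouts occur after randomisation the analysis set could approach 53: with 54 patients, failure was 22% at 30/20/10% and 1% at 50/35/25%. Separation is visible when it occurs, counts per arm can still be reported, and this is one of twelve secondary endpoints in an exploratory pilot. All of that stands. It limits the weight of the point but supplies no workable method.

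Four stronger readings are tempting, and the documents do not support them.

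- *The model will often fail.* No rescue rate is given. At overall rates of 37% or more an arm coefficient fails in only 1-3% of trials, and the other failures concern a covariate, chiefly a rare abnormal BET (section III, exclusion 8 removes patients with known pelvic floor dysfunction).
- *Six slopes are the cause.* At low rates an arm-only model fails on the arm terms almost as often. The covariates add further failures and most of the exaggeration: arm-only models overstate by 2-7% at 37% or more.
- *The effect is always overstated when the model fits.* At 30/20/10% the CSP01 estimate is close to the truth, and at 20/10/5% it is too small.
- *Rescue use would be paired with a run-in value capped by design.* Exclusion 4 removes "Patients reporting laxative, enema, and/or suppository usage for >2 days or any usage of a prohibited medication during the Run-in period". But item 4.b.ii does not clearly require pairing a yes/no variable, use on up to 2 days still allows both baseline values, and a paired analysis would be a different model from the one examined here.

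**Conclusion.** The concern holds in conditional form. The ceiling of 3.7 events per slope needs only 45 patients, a yes/no endpoint and the carried-over covariates. The consequences also depend on the unknown rescue rate and on assumed covariate prevalences and effects.

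With low to moderate use, the risk is an odds ratio that cannot be estimated: roughly 15-60% of trials at 40/25/15% to 30/20/10%. With heavier use, the risk is an arm log odds ratio too large by roughly 15-30% on average. That bias is modest beside the sampling error (0.25 against an SD of 1.07 in the 50/35/25% run above), so the result would be imprecise under any method.

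This is a low-severity improvement. The primary analysis and its power calculation are unaffected.

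**What to change.** In section VI, item 4.b.ii:

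1. Define the endpoint as any rescue laxative use during the treatment period (yes/no), and state which of the products named in section V.b, item 2 count.
2. Replace ordinary logistic regression for this endpoint with Firth-penalised logistic regression on arm and CIC/IBS-C stratum, with a penalised-likelihood 95% confidence interval. An exact test stratified by CIC/IBS-C is an alternative.
3. Report the number of users and the days of use per arm beside it.

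The other planned covariates may stay. Under the assumptions of the run with SD 1.07, six-slope Firth regression never failed and averaged -1.14 against -1.10 (SD 0.94). With arm and stratum only, it averaged -1.07 (SD 0.82). Dropping age, sex and BET is therefore a choice about precision and not needed for the repair.

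The cost is a sentence or two and standard software. The downside is slight shrinkage towards zero when very few patients use rescue.

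### The before/after rule makes no exception for rescue laxatives or overall relief: a change in rescue use would rise artefactually and a change in relief may lose precision, though the comparison between arms stays unbiased

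*Combined protocol and SAP*

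**What the plan says.** **Primary analysis (VI.4.b.i).** "Colonic transit times will be compared in a paired fashion for individual patients before and after the intervention", by repeated measures ANOVA "using a 3x2 design to distinguish between the outcomes of the three different groups", with a supporting regression on change in transit time.

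**Secondary analysis (VI.4.b.ii).** The whole rule is one sentence: "The secondary endpoints will be compared in a similar fashion", to which it adds a logistic regression that adjusts for confounders.

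**Endpoints (V.c, Data to be collected, item 2).** The list of twelve includes overall relief on a 0–10 scale and "Need for rescue laxatives". Neither has a unit, time window or baseline. Balloon expulsion, PAC-SYM and PAC-QOL are labelled as before/after or change; these two are not.

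**Run-in.** Exclusion 4 in Section III removes "Patients reporting laxative, enema, and/or suppository usage for >2 days" during run-in. Run-in lasts two weeks (V.a.2) and treatment three (V.a.3). Randomization at Day 0 follows a recheck of the entry criteria.

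**Rescue access.** The run-in text (V.a.2) describes contact with the investigator after five days without a bowel movement. V.b.2 repeats that rule and also says that "all patients will be able to receive laxative doses as needed at their request throughout the study".

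**Diary.** The daily diary, scheduled from Day -14, includes overall relief. Its listed items (V.a.3.e) do not include rescue use.

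**The concern.** A paired analysis needs a before value that measures the same thing as the after value.

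For rescue use it does not. Patients enter only if their run-in use was low, and nothing similar limits use on treatment. Regression to the mean then produces a rise in every arm even if nothing changes, and the longer treatment window inflates raw counts as well. A reader shown a significant time effect, or within-arm changes, could conclude that patients needed more laxatives on the product. Section VI.4.c also hopes to combine transit data with the secondary endpoints to find a meaningful transit threshold. If that work uses within-patient changes, the artefact does not cancel there.

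For relief, the item wording and the state against which relief is judged are not given, so it is unclear what a score before any treatment means. Subtracting a weakly related score costs precision, which matters with 15 patients per arm.

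**Working it through.** **1. The plan's own figure.** The documents give no figure for these two endpoints. The only power statement is for transit time, and it shows which test the 3x2 design rests on. The inputs are changes of 0, 10 and 13 h, SD 12 h, correlation 0.7, N = 45 and two-sided 5% (assumed; alpha is not stated).

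- The variance of the three means is (58.78 + 5.44 + 28.44)/3 = 30.89.
- The noncentrality of the arm-by-time F test is 45 × 30.89 / (2 × 0.3 × 144) = 16.1 on 2 and 42 df.
- Power is 94.3%, against the stated 94%.

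The powered test is therefore arm by time, not the time effect.

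**2. Rescue, no true change.** Assumptions, none from the documents:

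- each patient has one daily probability of use, the same before and after;
- days are independent;
- probabilities are Beta(1, b) across patients;
- entry requires at most 2 of 14 days.

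Simulation of 2 million patients per row gives:

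| Mean daily use before the cap | Run-in days/week | Treatment days/week | Ratio | Any use, 14 d vs 21 d |
|---|---|---|---|---|
| 0.05 | 0.25 | 0.31 | 1.24 | 38% vs 50% |
| 0.10 | 0.35 | 0.50 | 1.42 | 51% vs 63% |
| 0.15 | 0.40 | 0.61 | 1.52 | 57% vs 69% |
| 0.20 | 0.43 | 0.69 | 1.59 | 60% vs 72% |

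Raw counts carry a further factor of 21/14 = 1.5, so they rise 1.24 × 1.5 = 1.86 to 1.59 × 1.5 = 2.39 times. A nominal 5% paired test pooled over 45 patients rejects in about 13% to 77% of trials on weekly rates, and in about 67% to over 99% on raw days.

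A second set of assumptions (0.5 to 2 uncapped days per week, varying spread between patients) gives ratios of 1.26 to 2.23. The direction is stable; the size depends on the inputs.

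Inclusion 5 speaks of a 7-day run-in baseline. If the before window and the cap both cover 7 days, the ratios under that second set are 1.08 to 1.50 and the window factor is 21/7 = 3.

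**3. Does it reach the arm comparison?** I simulated trials of 15 per arm with the cap applied before randomization, at 1 or 2 uncapped days per week.

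- With no effect, arm by time rejects in 5.3% to 5.4% of trials, with a mean arm difference of about 0.
- With no effect, a treatment-period-only comparison rejects in 4.7% to 4.8%.
- The pooled time effect rejects in 36% to over 99% of the same null trials.
- If one arm's use is halved, power on change versus treatment period only is 34.4% vs 35.0%, 17.0% vs 13.1% and 65.3% vs 67.0%.

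**4. Relief.** Let k = SD before / SD after and ρ the correlation between the two scores. Then Var(change)/Var(after) = 1 + k² − 2ρk, which exceeds 1 only if k > 2ρ. For k = 1 the SE ratio is √(2(1 − ρ)). The covariate-adjusted SE ratio is √(1 − ρ²) in large samples. Power is for a 1-SD difference between two arms of 15 (noncentral t, two-sided 5%).

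| ρ | SE ratio, change | Power, change | SE ratio, covariate |
|---|---|---|---|
| 0 | 1.41 | 46% | 1.00 |
| 0.3 | 1.18 | 61% | 0.95 |
| 0.5 | 1.00 | 75% | 0.87 |
| 0.7 | 0.77 | 93% | 0.71 |

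Treatment-period scores alone give 75%. If run-in relief is nearly constant (k near 0), the variance ratio is 1.0 and nothing is lost. The plan's 0.7 is for transit time and cannot be carried over to relief.

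**The case against.** **The sentence may not mean a paired analysis here.** It goes on to logistic regression, which suits a yes/no rescue outcome compared between arms, and the endpoint list labels other items as change but not these two. This stands as an ambiguity. It does not settle the matter: spontaneous bowel movement frequency is also unlabelled, and a logistic model would still need a stated window.

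**The randomized comparison is sound.** A reader might infer that the false-positive rates above apply to the efficacy conclusion. They do not. Exclusion 4 acts on all arms before randomization, and the 3x2 design exists to separate the groups. Those rates belong to a before/after test that the plan does not name as its efficacy conclusion.

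**Rescue access is not a clean contrast.** One could infer strict access in run-in and free access on treatment. V.b.2 repeats the five-day rule, and its on-request sentence covers the whole study. The texts conflict, so no size should be attached to a change in access.

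**The rescue model is assumed.** Independent daily use ignores the five-day rule. If rescue were taken only under that rule, about two uses would fit into 14 days and the cap would seldom bind. The rise in weekly rate would then be smaller; the 1.5-fold window effect on raw counts would remain.

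**Noise in relief is conditional.** It is tempting to say that subtraction adds noise outright. The documents give neither the correlation nor the run-in spread, so only the condition can be stated.

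**Conclusion.** The point holds in limited form. The plan extends a before/after comparison to two endpoints without defining their before values. For rescue, any time effect or within-arm change is open to an artefactual rise: about 1.2 to 1.6 times on weekly rates under assumed daily use of 0.05 to 0.20 with the cap binding, and a further 1.5 times on raw counts. For relief, a change score loses precision when k > 2ρ, which is ρ < 0.5 with equal SDs; it loses nothing if run-in scores are near constant and gains if ρ > 0.5.

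The documents do not support the stronger reading that the comparison of CSP01 with CMC or placebo is biased. These are two unpowered secondary endpoints in an exploratory pilot, so what is at stake is interpretation and some precision, not the trial's main result.

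**What to change.** Add to VI.4.b.ii, in substance: overall relief and need for rescue laxatives are compared between arms on treatment-period values (Day 1 to Day 21). Relief is the mean daily score. Rescue is any use, or days with use per week of follow-up, taken from the recorded rescue administrations. The run-in value, where available, enters as a covariate and is not subtracted. No before/after test is interpreted for these two endpoints. State which model applies to each, so that the reference to logistic regression is clear. Keep the paired layout for endpoints with a true baseline.

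Name the source of the rescue data, since the listed diary items omit it; days per week of follow-up needs dated records. Give the relief item's wording and reference period. V.a.3.e calls the diary scale nominal and V.c.2 numerical; reconcile these.

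The rescue-access texts in V.a.2 and V.b.2 should be reconciled. So should the V.a.2 allowance for laxatives at a stable dose and the Exclusion 4 limit, because each affects what the rescue endpoint counts.

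The cost is a few sentences, and no new data provided that rescue administrations are recorded with dates. The downside is losing a before/after description for two endpoints. In large samples the covariate analysis is never less precise than either change scores or treatment-period scores alone.

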This is a randomized, double-blind, single-center clinical exploratory pilot comparing treatment with CSP01 to standard control (CMC) to placebo (sucrose) for prevention of constipation in patients with chronic idiopathic constipation. Notably, there is no data either from the wireless motility capsule or from radio-opaque marker transit studies establishing a clinically-meaningful threshold for change in transit time in response to any colonic motility agent, and our hope is that transit data combined with patient-reported outcomes (our secondary endpoints) from this pilot study would provide a meaningful transit improvement threshold that may be used in future research as well. There is some data demonstrating the effect of dietary fiber on colonic transit time.⁷ If we extrapolate data from the trial of dietary fiber on colonic transit time, which demonstrated a 10-hour difference in colonic transit time with a standard deviation of 12 hours, we would assume the same effect for our standard fiber (CMC) group. Assuming that CSP01 would give an additional 3-hour decrease in colonic transit over conventional fiber, our current sample size would have 94% (with $\geq 90\%$ considered excellent) power to detect a difference. Even with 30 total subjects, we would still have 80% power (see graph below which varies the sample size).

Power Analysis/Sample Size Determination.
For a Repeated Measures Anova with Indicated Specifications, & Assuming
A Test-Retest Correlation of 0.7

If we are more conservative with the effect of CSP01 over standard fiber and decrease the additional effect to 1 hour decreased colonic transit time (1/3 of what

we would expect), we would still have 88% power with our current sample size.

VII. Risks and discomforts

1. Device side effects and adverse events

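### The 94% and 88% powers quoted beside a 3-hour and a 1-hour CSP01 advantage over fiber belong to the three-arm omnibus test; power for CSP01 versus CMC is about 14% and 6%

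*Combined protocol and SAP*

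**What the plan says.** Section IV.c randomizes 1:1:1 to CSP01, CMC and placebo, 15 per arm. Section VI.4.b names the primary analysis of colonic transit time as a "repeated measures ANOVA using a 3x2 design to distinguish between the outcomes of the three different groups".

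Section VI.4.c builds its power on a fiber trial "which demonstrated a 10-hour difference in colonic transit time with a standard deviation of 12 hours" and assigns that effect to the CMC arm. The 94% is introduced by "Assuming that CSP01 would give an additional 3-hour decrease in colonic transit over conventional fiber" and is described as "power to detect a difference". With 30 patients in total the stated figure is 80%. The paragraph then offers a more cautious case, to "decrease the additional effect to 1 hour decreased colonic transit time", and concludes that "we would still have 88% power with our current sample size". The graph caption names a repeated measures ANOVA and assumes "A Test-Retest Correlation of 0.7". The available text states no alpha, no placebo change and no source for the 0.7. The graph itself was not available.

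**The concern.** Two things in this paragraph invite a wrong conclusion.

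First, each power is tied in the prose to the size of CSP01's advantage over fiber. A reader will take it that 45 patients can detect 3 hours over CMC with 94% power, or even 1 hour with 88%. A drop of only six points when the increment shrinks to a third suggests that the increment is not what drives the power.

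Second, the level of the power depends on one assumed correlation with no stated support.

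The aim in section II sets CSP01 against an active control as well as placebo. If the power is misattributed, a non-significant CSP01-versus-CMC comparison may be read as evidence of no advantage, and a significant three-arm test may be read as showing one.

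**Working it through.** **Inputs.** From VI.4.c: CMC change 10 h; CSP01 change 13 h (10 + 3) or 11 h (10 + 1); SD 12 h; correlation 0.7. From IV.c: n = 15 per arm. Assumed here because not stated: two-sided alpha 0.05 and placebo change 0 h. Both are supported by the match below.

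**Step 1: reproduce the stated figures.** In a 3x2 repeated measures design the group-by-time test equals a one-way ANOVA on change.

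- SD of change = 12 × √(2 × (1 − 0.7)) = 12 × √0.6 = 9.295 h, squared 86.4.
- Noncentrality λ = n × Σ(μᵢ − μ̄)² / SD², with 2 and 3(n − 1) df.

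| Mean changes (placebo/CMC/CSP01) | n per arm | Σ(μᵢ − μ̄)² | λ | Power | Stated |
|---|---|---|---|---|---|
| 0/10/13 | 15 | 92.67 | 16.09 | 94.3% | 94% |
| 0/10/11 | 15 | 74.00 | 12.85 | 88.2% | 88% |
| 0/10/13 | 10 | 92.67 | 10.73 | 79.8% | 80% |

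All three agree, so the stated figures are omnibus powers with 12 h as the SD of a single measurement.

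**Step 2: find where that power comes from.** The sum of squares splits into two parts: the mean of the active arms against placebo, (2/3) × (mean active change)², and CSP01 against CMC, (difference)²/2.

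- 3-hour case: (2/3) × 11.5² = 88.17, plus 3²/2 = 4.5, total 92.67. CSP01 versus CMC supplies 4.5/92.67 = 4.9%.
- 1-hour case: (2/3) × 10.5² = 73.5, plus 1²/2 = 0.5, total 74. CSP01 versus CMC supplies 0.5/74 = 0.7%.
- CSP01 exactly equal to CMC (0/10/10): sum 66.67, λ = 15 × 66.67/86.4 = 11.57, power 84%.

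**Step 3: power of the pairwise contrasts.** Noncentral t with 42 df, critical value 2.018, standard error = SD × √(2/15). That is 3.39 h at SD of change 9.3 h and 4.38 h at 12 h.

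| Contrast | True difference | Power, SD 9.3 h | Power, SD 12 h |
|---|---|---|---|
| CSP01 vs CMC | 3 h | 14% | 10% |
| CSP01 vs CMC | 1 h | 6% | 6% |
| CSP01 vs placebo | 13 h | 96% | 83% |

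The difference detectable with 80% power is about 9.7 h at SD 9.3 h and 12.6 h at SD 12 h. The 95% confidence interval for CSP01 versus CMC would have a half-width of about 2.018 × 3.39 = 6.8 h, or 2.018 × 4.38 = 8.8 h.

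**Step 4: sensitivity to the correlation.** 12 h per measurement throughout.

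| Correlation | SD of change | N=45, +3 h | N=45, +1 h | N=30, +3 h |
|---|---|---|---|---|
| 0.7 | 9.3 h | 94% | 88% | 80% |
| 0.6 | 10.7 h | 86% | 77% | 67% |
| 0.5 | 12.0 h | 77% | 67% | 57% |

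The last row is numerically the same as taking 12 h to be the SD of change itself.

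**The case against.** The best defense is that the protocol makes no false statement. It claims power for a difference, names the repeated measures ANOVA, and specifies a three-group test. It nowhere says that it has pairwise power for CSP01 versus CMC; the 3 and 1 hours are inputs to one arm's mean. This stands as far as it goes. But the prose presents those hours as the effect under study and calls the smaller one the cautious case, and nothing in the available text warns that the contrast with CMC is almost uninformative.

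A reader might infer something stronger: that 12 h is grammatically the SD of the 10-hour difference, so the true powers are 77%, 67% and 57% and the stated ones are miscalculated. The documents do not support that. A test-retest correlation has a role only if 12 h is the SD of a single measurement, and on that reading all three figures reproduce. The sentence can also mean a difference on a scale whose SD is 12 h. The lower figures are therefore a sensitivity case. The missing graph may define the SD and alpha, so their absence from the text is not held against the plan.

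A reader might also infer that the trial is too small. It is labelled an exploratory pilot, the protocol says that no clinically meaningful transit threshold exists, and power for the assumed 13-hour CSP01-versus-placebo difference is 96%, or 83% at the larger SD.

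**Conclusion.** The concern holds as a misattributed power statement resting on an unsupported variance assumption, not as an arithmetic error. The 94%, 88% and 80% are correct for the omnibus group-by-time test on the protocol's inputs, but they say almost nothing about CSP01 against CMC. For that contrast power is about 14% or less on either SD, and the detectable difference is more than three times the assumed 3 hours (9.7/3 = 3.2; 12.6/3 = 4.2). This part does not depend on what the 12 h describes.

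The omnibus level does depend on the correlation: at N=45 with the 3-hour increment it drops from 94% to 86% at 0.6 and 77% at 0.5. The results assume alpha 0.05, no placebo change, 15 analyzed per arm and equal variances across arms. What is at stake is what the trial may claim about its active control.

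**What to change.** In section VI.4.c:

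1. Label the 94%, 88% and 80% as power of the omnibus group-by-time test under the assumed means, with alpha and the placebo change stated.
2. State that power for CSP01 versus CMC is about 14% or less for the assumed increments, that this contrast will be estimated with a confidence interval, and that a null result is not evidence of no advantage.
3. Give the omnibus power as a range over correlation 0.5 to 0.7: 77–94%, 67–88% and 57–80% for the three cases. In the same sentence, say which quantity the 12 h describes and what supports the 0.7.

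The cost is the rewording of one paragraph and a less favorable stated power. Sample size, conduct and the primary test stay as they are.
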